**Population-level summary:**

- **polyTreg infusion reactions** – mITT2
- **Acute rejection using Banff grading** – mITT1, subset to participants that have available Banff lab data
- **Acute rejection after converting to mTOR therapy after polyTregs infusion** - mITT2
- All other endpoints will use the mITT1 sample

**Variable:** Secondary severity endpoints including:

Endpoint	Time Frame
polyTreg infusion reactions	405 days post-group allocation
Culture-proven and clinically diagnosed infections	405 days post-group allocation
Acute rejection using Banff grading	405 days post-group allocation

**Analysis:** For each of the above severity endpoints, the count of participants will be reported by treatment group and compared using Fisher's Exact test or a Cochran-Mantel-Haenszel test.

**Population-level summary:**

- **polyTreg infusion reactions** – mITT2

- **Culture-proven and clinically diagnosed infections** – mITT1, subset to those with culture-proven and clinically diagnosed infections
- **Acute rejection using Banff grading** – mITT1, subset to participants that have available Banff lab data

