14.3. Grading and Attribution of Adverse Events

14.3.1. Grading Criteria

The study site will grade the severity of adverse events experienced by the study subjects according to the criteria set forth in the National Cancer Institute's Common Terminology Criteria for Adverse Events (CTCAE) *version 4.0*.

This document (referred to herein as the NCI-CTCAE manual) provides a common language to describe levels of severity, to analyze and interpret data, and to articulate the clinical significance of all adverse events. The NCI-CTCAE has been reviewed by the principal investigator and protocol chair and has been deemed appropriate for the subject population to be studied in this protocol.

Infections will be graded using the study-specific scale as described below:

Grade 1 = asymptomatic; clinical or diagnostic observation only; intervention with oral antibiotic, antifungal, or antiviral agent only; no invasive intervention required

Grade 2 = symptomatic; intervention with intravenous antibiotic, antifungal, or antiviral agent; invasive intervention may be required

Grade 3 = any infection associated with hemodynamic compromise requiring pressors; any infection necessitating ICU level of care; any infection necessitating operative intervention; any infection involving the central nervous system; any infection with a positive fungal blood culture; any proven or probable aspergillus infection; any tissue invasive fungal infection; any pneumocystis jiroveci infection

Grade 4 = life-threatening infection

Grade 5 = death resulting from infection

All other adverse events will be graded on a scale from 1 to 5 according to the following standards in the NCI-CTCAE manual:

Grade 1 = mild adverse event.

Grade 2 = moderate adverse event.

Grade 3 = severe and undesirable adverse event.

Grade 4 = life-threatening or disabling adverse event.

Grade 5 = death.

Infection events grade 2 or higher; and all other events CTCAE grade 2 or higher will be recorded on the appropriate AE eCRF for this study.

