15.3.2. Endpoint Assessments

15.3.2.1 Primary and Secondary Safety Endpoints

Table 7. Analyses of Safety Endpoints describes the safety endpoints and their corresponding parameters to be estimated in the study. Safety endpoints will be listed or summarized, as appropriate, using standard descriptive statistics for continuous and categorical data.

Table 7. Analyses of Safety Endpoints

ENDPOINT	DESCRIPTIVE PARAMETER	ANALYSIS POPULATION
Primary Endpoint		
Incidence of severe acute rejection or antibody mediated rejection in subjects receiving polyTregs in comparison with CNI-based maintenance IS therapy.	Proportion with exact binomial 95% confidence limits	miITT1
Incidence of severe infection in subjects receiving polyTregs in comparison with CNI-based maintenance IS therapy.	Proportion with exact binomial 95% confidence limits	miITT1
Secondary Endpoints – Treg safety		
Incidence of polyTregs infusion reactions (episodes of fever, bronchospasm, hypoxia, cytokine release syndrome, or infusion site reaction)	Proportion with exact binomial 95% confidence limits	miITT2
Severity of polyTregs infusion reactions	Descriptive CTCAE categories	miITT2
Incidence of culture-proven and clinically diagnosed infections	Proportion with exact binomial 95% confidence limits	miITT1
Severity of culture-proven and clinically diagnosed infections	Descriptive CTCAE categories	miITT2
Incidence of severe infection in subjects receiving polyTregs in comparison with CNI-based maintenance IS therapy.	Proportion with exact binomial 95% confidence limits	miITT1
Timing of acute rejection	Mean time to rejection and standard deviation	miITT1
Incidence of acute rejection	Proportion with exact binomial 95% confidence limits	miITT1
Severity of acute rejection	Descriptive Banff criteria	miITT1
Incidence of CMV reactivation	Proportion with exact binomial 95% confidence limits	miITT1
Incidence of BK viremia	Proportion with exact binomial 95% confidence limits	miITT1
Incidence of >10% decrease in eGFR from baseline	Proportion with exact binomial 95% confidence limits	miITT1
Secondary Endpoints – mTOR therapy		
Incidence of acute rejection	Proportion with exact binomial 95% confidence limits	miITT2 (Treg mTOR vs Treg no mTOR)

15.3.2.2 *Supportive Analyses of the Primary Safety Endpoints*

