### **9.3. Adverse Events**

All AEs will be classified by system organ class (SOC) and preferred term, according to a standardized thesaurus (Medical Dictionary for Regulatory Activities [MedDRA] version 18.1). The severity of AEs will be classified using the National Cancer Institute's (NCI's) Common Toxicity Criteria for Adverse Events (CTCAE) version 4.0. Each AE is entered on the electronic case report form (eCRF) once at the highest severity. As such, no additional data manipulation is needed to identify events.

A summary table will present the total number of events as well as the number and percentage of subjects experiencing the events organized by relatedness and severity for all AEs and SAEs separately. If a subject experiences the same AE on multiple occasions, the event will be counted once for each occurrence when reporting the number of AEs. When reporting the number of subjects experiencing the events, a subject will only be counted once if they experience an event within the particular SOC or preferred term. A data listing will be provided for all AEs. Separate listings will be provided for the CSR as needed.

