## **10. CHANGES TO THE ANALYSES PLANNED IN THE PROTOCOL**

The analysis populations for the endpoints 1) incidence of severe acute cell-mediated rejection and/or acute antibody mediated rejection, 2) incidence of acute rejection, 3) severity of acute rejection, and 4) timing of acute rejection were changed from the modified intent-to-treat population to the modified intent-to-treat population subset to participants that have available Banff data.

The analysis population for the severity of culture-proven and clinically diagnosed infections endpoint was changed from the modified intent-to-treat population with polyTregs infusion to the modified intent-to-treat population subset to those with culture-proven and clinically diagnosed infections.

The analysis populations for the endpoints 1) percent change in inflammation at 7 months after group allocation relative to baseline biopsy and 2) proportion of participants exhibiting  $\geq 25\%$  relative decrease of inflammation between baseline kidney biopsy and the 6 month kidney biopsy were changed from the modified intent-to-treat population with polyTregs infusion to the modified intent-to-treat population subset to participants that have available LCA data from 6 month visit.

The analysis populations for the endpoints 1) proportion of participants exhibiting  $\geq 25\%$  relative decrease of inflammation between baseline kidney biopsy and the week 2 kidney biopsy and 2) proportion of participants exhibiting  $\geq 50\%$  relative decrease of inflammation between baseline kidney biopsy and the week 2 kidney biopsy were changed from the modified intent-to-treat population with polyTregs infusion to the modified intent-to-treat population subset to participants that have available LCA data from Week 2 visit.

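### Infection severity is compared between arms only among infected participants, so the arm with fewer grade 2 infections can show the higher severe share when severe-infection risk is equal

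*SAP*

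**What the plan says.** **Protocol.** Table 7 (Section 15.3.2.1) lists "Severity of culture-proven and clinically diagnosed infections" with descriptive CTCAE categories as the parameter and mITT2, the polyTreg recipients, as the population. Section 3.3.1 frames the secondary safety endpoints, infection severity among them, as a description of Group 2 alongside Group 1. Section 15.5 says that secondary endpoints will be handled descriptively and not by statistical comparison of the groups. Section 14.3.1 sets the grading rule: "Infections will be graded using the study-specific scale as described below". CTCAE is kept there for all other events, and only infections of grade 2 or above go on the adverse event form.

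**SAP.** For the severity endpoints in 8.2.1, "the count of participants will be reported by treatment group and compared using Fisher's Exact test or a Cochran-Mantel-Haenszel test". The population for infection severity is "mITT1, subset to those with culture-proven and clinically diagnosed infections". Section 10 confirms that this was deliberate: "The analysis population for the severity of culture-proven and clinically diagnosed infections endpoint was changed from the modified intent-to-treat population with polyTregs infusion" and now runs "to the modified intent-to-treat population subset to those with culture-proven and clinically diagnosed infections". Section 10 does not mention that a between-arm test has been added.

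**Grading scale in the SAP.** Section 8.1.1 describes severe infection on the study-specific scale. Section 9.3 states, without an exception for infections, "The severity of AEs will be classified using the National Cancer Institute's (NCI's) Common Toxicity Criteria for Adverse Events (CTCAE) version 4.0". Section 8.2.1 names no scale for this endpoint.

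**The concern.** The infected-only population is not a missing-data subset like the Banff or LCA subsets elsewhere in the SAP. It is defined by an outcome that occurs after allocation and that a suppressive cell product could plausibly change; Protocol 9.1.1 lists infection as a potential risk of the cells. Within that subset, an arm's severe share is severe / (severe + grade 2). It moves when the number of grade 2 infections moves, even if severe infection is unchanged. Fewer grade 2 infections raise the share and more lower it, so the table can point away from the comparison of arm risks.

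At stake is how a safety table is read in a trial of 14 people, where the displayed percentages will carry more weight than any p-value. The severe-or-not and any-or-none comparisons are made elsewhere on full arms. The full grade distribution by arm, including grade 3 against grade 4, is compared only here.

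**Working it through.** **Inputs from the documents.** 7 per arm (Protocol 15.5). Recorded infections are grade 2 or higher (Protocol 14.3.1), so the milder infections in this table are grade 2. Two-sided 0.05 is stated only for the efficacy power calculation; no level is stated for safety tests, and it is used here as a reference. The documents give no infection rate or grade distribution, so there is no planned figure to reproduce, and every infection count or rate below is an assumption.

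**Step 1: equal severe counts, unequal grade 2 counts.** Subset share = s / infected; arm risk = s / 7.

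| Severe in each arm | Infected, Group 1 v Group 2 | Subset share | Arm risk | Subset Fisher p |
|---|---|---|---|---|
| 1 | 5 v 2 | 1/5 = 20% v 1/2 = 50% | 14.3% v 14.3% | 1.00 |
| 1 | 6 v 2 | 17% v 50% | 14.3% v 14.3% | 0.46 |
| 2 | 6 v 3 | 33% v 67% | 28.6% v 28.6% | 0.52 |
| 2 | 7 v 2 | 29% v 100% | 28.6% v 28.6% | 0.167 |

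The full-arm Fisher p is 1.00 in every row. In the opposite direction, 5 v 6 infected with one severe each gives 1/5 = 20% v 1/6 = 17%. That shift is small and amounts to one participant.

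**Step 2: can equal severe counts give a small p?** All tables of severe against grade 2 with equal severe counts and at most 7 infected per arm were enumerated.

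- Fisher: the smallest p comes from 2/7 v 2/2. With 4 severe among 9 infected, the probability that both infected in the smaller group are severe is C(4,2)/C(9,2) = 6/36 = 0.167, and no other outcome is as unlikely.
- Unstratified Cochran-Mantel-Haenszel, statistic (N−1)(ad−bc)² / (product of the four margins): the smallest p comes from 1/7 v 1/1. The statistic is 7 × (1×0 − 6×1)² / (7×1×2×6) = 252/84 = 3.0 on 1 df, p = 0.083.

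Neither test reaches 0.05.

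**Step 3: equal severe risk, with counts free to vary.** Exact enumeration of severe / grade 2 / none, 7 per arm. Group 2 is the arm with fewer grade 2 infections.

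| Severe risk, both arms | Grade 2 risk, Group 1 v Group 2 | P(Group 2 has higher subset share) | P(Group 2 has higher full-arm severe rate) | P(Fisher p<0.05), subset v full arm |
|---|---|---|---|---|
| 10% | 50% v 20% | 0.46 | 0.31 | 1.1% v 0.02% |
| 14.3% | 57.1% v 14.3% | 0.60 | 0.34 | 3.6% v 0.07% |
| 20% | 60% v 20% | 0.68 | 0.37 | 4.4% v 0.22% |
| 28.6% | 71.4% v 14.3% | 0.84 | 0.38 | 8.5% v 0.6% |

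On full arms the chance of a higher rate is the same for both groups. In the subset it tilts towards the arm with fewer grade 2 infections. Small p-values are possible here because observed severe counts can differ by chance. The last row assumes everyone in Group 1 is infected, so it is an extreme case.

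**The case against.** The strongest reply is that severe-infection risk is already measured without conditioning. Under SAP 8.1.2, grade 3 or higher infection is a primary safety endpoint compared on full mITT1. Under 8.2.1, any infection is compared on full mITT1. In the 5 v 2 example those outputs would show 1/7 v 1/7 and 5/7 v 2/7. Study-defined grade 4 or higher infection is a stopping criterion in Protocol 13.3, and all adverse events are listed. SAP 7.1.4 calls the analysis mainly descriptive. This stands: it limits the harm to one secondary table. It does not repair that table, and the cross-check works only for a reader who puts three outputs together.

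Second, showing both arms agrees with Protocol 3.3.1, and Protocol 15.3.3 allows simple tests across groups for reported adverse events. This also stands. The fault lies in the conditioning and the undeclared test, not in bringing Group 1 into the display.

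Third, severity exists only for events, so grades among the infected are a natural description. That is fair for a listing. It does not justify a between-arm test on that subset.

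Fourth, the CTCAE wording has no demonstrated effect on a result, since SAP 8.1.1 already uses the study scale for severe infection. Agreed: it is mainly a labelling conflict.

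A reader might infer that the plan assesses severe infection only among infected participants, or that it would misstate the trial's severe-infection risk. The documents do not support either reading, because the primary endpoint uses full mITT1.

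**Conclusion.** The point holds for one secondary endpoint. Testing infection severity among infected participants conditions on a post-allocation outcome, and equal severe risk can be displayed as 20% v 50%, or in a more extreme table as 29% v 100%. The damage is mainly to displayed percentages. With equal observed severe counts and 7 per arm, p does not fall below 0.167 by Fisher or 0.083 by unstratified Cochran-Mantel-Haenszel. With equal underlying risk and strongly contrasting assumed grade 2 rates, subset p<0.05 occurs 1.1% to 8.5% of the time, so a general claim of false significance would overstate the case.

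The direction of the distortion follows from the arithmetic; its size rests on assumed infection rates. The p-value results assume 7 per arm and grades collapsed to severe against grade 2. A test across all separate grades was not enumerated. The undeclared test and the scale labels are documentation faults alongside this.

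**What to change.** - **SAP 8.2.1.** Tabulate the worst infection grade on the study-specific scale for every mITT1 participant by arm, with none recorded as the lowest category. That category suits a form that does not capture grade 1. Give cumulative counts (any recorded, grade 3 or higher, grade 4 or higher) over the full arm with exact 95% intervals; for 1/7 the interval is 0.4% to 57.9%. Keep grades among infected participants as a descriptive listing without a p-value.
- **SAP Section 10.** Update the population statement. If any between-arm severity test is kept, declare it there and reconcile it with Protocol 15.5.
- **Protocol Table 7 and SAP 9.3.** Label infection severity with the study-specific scale, in line with Protocol 14.3.1 and SAP 8.1.1.

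The cost is wording and table shells, with no new data. The downside is some overlap with the incidence endpoints already planned, since two of the three cumulative counts repeat them.

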### **8.3. Other Endpoints**

Any mechanistic data received, aside from data that's been noted above in sections 8.1 and 8.2, will be summarized using appropriate statistics, provided that the data is sufficient and complete to do so.

## **9. SAFETY EVALUATION**

### **9.1. Overview of Safety Analysis Methods**

General safety analyses will be carried out using the mITT1 population defined in Section 4 (with the addition of the one subject who received darTregs), unless otherwise noted. Missing safety information will not be imputed. These analyses will not be stratified by site.

Safety will be analyzed in each treatment group through the reporting of AEs, vital signs, and changes in routine laboratory measures.

Listings will be prepared, if needed to fulfill regulatory reporting obligations, for all safety measurements. All listings will be sorted in order of subject identifier and time point of assessment (e.g., visit and/or time).

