13.1. Participant Stopping Rules and Withdrawal Criteria

Participants may be prematurely terminated from the study for the following reasons:

1. The participant elects to withdraw consent from all future study activities, including follow-up.
2. The participant is “lost to follow-up” 3 months after the date of a missed study visit (i.e., no further follow-up is possible because attempts to reestablish contact with the participant have failed).
3. The participant dies.
4. The Investigator no longer believes participation is in the best interest of the participant.
5. CTCAE Grade 3 or higher infusion reaction.
6. Failure to manufacture and supply the cellular product two times for the same subject.

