13.3. Study Stopping Rules

The study may be prematurely terminated for the following reasons:

1. Any CTCAE grade 4 or higher infusion reaction
2. Any study defined grade 4 or higher infection
3. Any diagnosis of malignancy and post-transplant lymphoproliferative disease (except non-melanoma skin cancer)
4. Any graft loss
5. Acute Rejection (Banff grade 2A or higher) or acute antibody mediated rejection within 6 weeks after Treg infusion in 3 of first 5 subjects
6. Any death
7. Inability to manufacture and supply polyTregs in 3 of 5 consecutive subjects assigned to Group 2
8. If there is a total of 8 failed lots of polyTregs at any time during the study.

Any of these events will stop trial enrollment and Treg infusions and require DSMB review (See Section 14.8). Subjects who have already received Treg infusion are eligible for mTOR therapy will remain on current therapy during the data review.

14. Safety Monitoring and Reporting

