14.4. Collection and Recording of Adverse Events**14.4.1. Collection Period**

Adverse events will be collected from the time of first study mandated procedure until a subject completes study participation or until 30 days after he/she prematurely withdraws (without withdrawing consent) or is withdrawn from the study.

Note that the study eligibility is performed as a standard of care surveillance biopsy with no collection of research specimens. The eligibility biopsy is not considered a study mandated procedure for these reasons.

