### 3. PROTOCOL SUMMARY

Title	Treg Adoptive Therapy in Subclinical Inflammation in Kidney Transplantation
Short Title	Tregs Infusion for Inflammation Suppression
Clinical Phase	I/II
Number of Sites	7
IND Sponsor/Number	NIH/NIAID/DAIT/ #16626
Study Objectives	

1. To assess the safety of polyTregs infusions and the safety of converting from CNI-based maintenance therapy to mTOR inhibitors after Treg therapy in adult kidney transplant recipients (see Study Definitions page).

2. To assess the efficacy of polyTregs infusions in reducing inflammation in adult kidney transplant recipients (see Study Definitions Page).

Study Design	
This is a multi-center, open-label, randomized, controlled safety and efficacy trial with 2 cohorts, maintenance CNI-based immunosuppression therapy and polyTregs infusion, to achieve inflammation suppression in adult kidney transplant recipients. Eligible participants will either continue maintenance CNI-based immunosuppression therapy or will receive a single infusion of polyTregs (<math>550 \pm 450 \times 10^6</math>). All participants will undergo biopsies to determine study eligibility and at 7 months after study group allocation. Participants who received a polyTregs infusion will undergo an additional biopsy 14 days after polyTregs infusion.
 
The original study design included a third treatment arm of donor alloantigen reactive Tregs (darTregs). One participant was treated with darTregs prior to protocol version 9.0 in which this treatment arm was eliminated due to excessive manufacturing failures.

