#### 4. ANALYSIS SAMPLES

**Modified Intent-to-Treat Sample 1 (mITT1)** – The mITT1 sample consists of all subjects allocated to the CNI-based treatment regimen or received polyTregs while on study.

**Modified intent-to-Treat Sample 2 (mITT2)** – The mITT2 sample consists of all subjects who received polyTregs (Group 2).

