### **6.2. Randomization**

Participants will be assigned to the treatment groups in an unblinded fashion using a variation of the Pocock and Simon adaptive randomization strategy. A web-based randomization system will be used in order to minimize the possibility of bias entering into those assignments and to maintain approximate equality in the group sizes. The initial treatment allocation will weight each treatment equally. In subsequent allocations, the less-populated arm will be weighted more in order to restore the balance between the groups. If a recipient is assigned to polyTreg and the recipient does not receive the intended polyTreg infusion, that recipient will be re-assigned to Group 1. The allocation schedule algorithm/scheme will not incorporate stratification variables.

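### The general safety summaries have no polyTreg or collection column for participants who underwent manufacturing collection but were never infused, so their collection harms are summarised under control or appear only in listings.

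*SAP*

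**What the plan says.** SAP 9.1 sets the default population for safety: "General safety analyses will be carried out using the mITT1 population defined in Section 4 (with the addition of the one subject". The added person is the single treated darTreg recipient, and the rule gives way wherever the SAP names another population. SAP 4 defines the base set: "The mITT1 sample consists of all subjects allocated to the CNI-based treatment regimen or received polyTregs while on study". The only other sample there is narrower: "The mITT2 sample consists of all subjects who received polyTregs (Group 2"). SAP 9.3 plans one summary table of AEs and SAEs by relatedness and severity and names no different population for it. It also promises a listing of all AEs, and SAP 9.4 lists SAEs.

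On data capture, Protocol 14.4.1 says: "Adverse events will be collected from the time of first study mandated procedure until a subject completes study participation". Protocol 8.1 and 8.2 place the 450-500 mL draw or leukapheresis after randomisation to Group 2 and allow the blood collection to be repeated once. Protocol 14.3.2 names leukapheresis and blood draw among the procedures assessed for attribution when an SAE is reported.

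On what happens when no product is infused, the documents give two routes. Protocol 3.7 and SAP 6.2 say of such a recipient "that recipient will be re-assigned to Group 1". Protocol 13.1 lists as a reason for premature termination "Failure to manufacture and supply the cellular product two times for the same subject", and 13.2 replaces anyone terminated before infusion.

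Manufacturing failure is foreseen. Protocol 13.3 has a rule for failure in 3 of 5 consecutive Group 2 subjects and another: "If there is a total of 8 failed lots of polyTregs at any time during the study". SAP 3 says of the darTreg arm that "this treatment arm was eliminated due to excessive manufacturing failures".

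**The concern.** The primary safety objective is the safety of polyTregs, and nobody can receive them without first undergoing collection. The data are gathered to match, because AE capture starts before infusion. The summaries do not match, because infusion is the condition for entering the polyTreg column.

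Three things follow. First, collection harms in participants who end without a product are missing from the column in which a reader would look for them. Second, if re-assignment applies, those harms are added to Group 1, which had no such procedure, so the contrast is distorted from both sides. Third, any complication of collection that itself led to no infusion would remove its own case from the polyTreg column. The documents do not say that this has happened, but the definition permits it.

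The same gap affects darTregs. SAP 9.1 adds back only the treated recipient. Participants assigned to darTregs whose product failed, if there were any, have no stated place in the summaries.

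This is a question of which AEs are displayed and under which exposure. It is separate from whether efficacy should be compared as randomised.

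**Working it through.** The plan gives no figure on this point, so there is none to reproduce. Its only design calculation is the efficacy power table, which does not bear on it. The check is a trace through the rules, followed by bounds.

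**Trace of one Group 2 participant whose product fails**

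| Step | Rule | Result |
|---|---|---|
| Randomised to Group 2, then collected | Protocol 8.1, 8.2 | Exposed to draw or leukapheresis |
| AE after collection | Protocol 14.4.1 | Recorded |
| Not infused: is the participant in mITT2? | SAP 4 | No |
| Not infused: in mITT1 as a polyTreg recipient? | SAP 4 | No |
| Route A: re-assigned | Protocol 3.7, SAP 6.2 | Counted in Group 1, if re-assignment counts as allocation to CNI (not stated) |
| Route B: terminated after two failures, replaced | Protocol 13.1, 13.2 | Outside mITT1; AEs only in the SAP 9.3 and 9.4 listings |

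Neither route places the event in the polyTreg column.

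**How many could be affected**

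Inputs: 7 infused participants (the accrual target); review triggered at 3 failures in 5 consecutive Group 2 subjects; review triggered at 8 failed lots (both Protocol 13.3). Let f be the number collected and never infused because manufacturing failed, in a sequence that ends at the seventh infusion.

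- To avoid the 3-of-5 rule, any 5 consecutive subjects may contain at most 2 failures.
- f = 6 is possible with one failed lot each. Writing F for failed and S for supplied, the sequence FFSSS FFSSS FFS has 6 F and 7 S, with never more than 2 F in any five in a row. Six failed lots is below 8.
- f = 7 is not possible. Fourteen subjects split into blocks of 5, 5 and 4, with at most 2 failures each: 2 + 2 + 2 = 6 < 7. An enumeration of all such sequences confirms that 6 is the maximum.
- Upper bound: 6 / (6 + 7) = 6/13 = 46%.
- If every affected participant had two failed lots, staying below 8 lots allows at most 3 participants (3 × 2 = 6; 4 × 2 = 8 triggers the rule): 3 / (3 + 7) = 30%.

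These bounds cover manufacturing failure only. Protocol 4.2 gives other grounds for not infusing, such as a positive SARS-CoV-2 or pregnancy test. Neither stopping rule counts those.

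**What one misplaced event does**

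Assume one collection harm in one never-infused participant. This is an illustration, not a document figure. Limits are exact (Clopper-Pearson) 95%.

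| Display | f = 1 | f = 3 | f = 6 |
|---|---|---|---|
| polyTreg column under SAP 9.1 | 0/7 (0 to 41.0%) | 0/7 | 0/7 |
| Group 1, route A, never-infused counted within 7 | 1/7 = 14.3% (0.4 to 57.9%) | 1/7 | 1/7 |
| All collected as denominator | 1/8 = 12.5% (0.3 to 52.7%) | 1/10 = 10.0% (0.3 to 44.5%) | 1/13 = 7.7% (0.2 to 36.0%) |

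Under route A, if re-assigned participants are added to 7 controls rather than counted within them, the Group 1 figure is 1/(7 + f). Under route B the event is in no column.

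**The case against.** The best case for the plan is that product safety is commonly grouped by product received, and that collection harms in infused participants stay in Group 2. The primary safety endpoints are severe rejection and grade 3 or higher infection, not collection harms. Protocol 9.4 describes mostly minor effects of collection, only AEs of grade 2 or higher are recorded (Protocol 14.3.1), and itemised attribution is tied to SAE reports. Re-assignment is worded as the rule and termination as an option, so the route to no column at all is probably the less common one. A re-assigned participant's event would at least be tabulated, and could show as related. All of this stands. It limits the size of the problem but leaves the never-infused in the wrong column or in none.

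A reader might infer more than the documents support:

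- **That every safety table is affected.** SAP 9.1 covers general analyses unless otherwise noted, and SAP 8.2 uses mITT2 or subsets of mITT1 for some endpoints. Those samples do not recover the missing participants either, but the statement would be too broad.
- **That the events are lost altogether.** SAP 9.3 promises a listing of all AEs (population not stated) and SAP 9.4 lists SAEs. Protocol 14.5.2.1 and 14.8.2 send AEs to the annual IND report and the DSMB. In a trial of 14 such listings matter, but they give no denominator or rate.
- **That 8 failed lots against 7 infused means 8 of 15 collected participants could go unseen.** For manufacturing failure this cannot happen before the 3-of-5 rule triggers: fifteen subjects form three blocks of five, and 8 failures must put at least 3 in one block. Eight lots would also trigger the lot rule itself.
- **That failed darTreg participants are known to exist.** The arm closed because of manufacturing failures, which makes it plausible, but no number or disposition is given.

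**Conclusion.** The concern holds for the general safety summaries. Under the stated rules, a participant assigned to Tregs, collected and never infused does not appear in the polyTreg column. The collection AEs are summarised under Group 1, or they appear only in listings if the participant was terminated and replaced. Failed darTreg participants, if any, have no stated place.

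The number affected is not given and may be small. For manufacturing failure, with 7 infused and neither stopping rule triggered, it is at most 6 of 13 collected polyTreg participants (46%), or 3 of 10 (30%) if each had two failed lots. The effect begins at one participant: 1/7 is about 14 points of a 7-person column. The Group 1 route assumes that a re-assigned participant counts as allocated to CNI, which the documents do not settle.

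This is a worthwhile, inexpensive correction to the safety display. It does not show that harm has been concealed.

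**What to change.** 1. In SAP 4 and 9.1, add a safety set of all randomised participants who began a study-mandated procedure, including those assigned to either Treg product and never infused.
2. In SAP 9.3, add a collection-phase AE column with all collected participants as denominator. Keep post-infusion AEs by product received.
3. Count a re-assigned participant's AEs under Group 1 only from the date of re-assignment.
4. Reconcile Protocol 3.7 and SAP 6.2 (re-assign) with Protocol 13.1 and 13.2 (terminate and replace), so that each never-infused participant has one stated disposition. Say whether a re-assigned participant belongs to mITT1.
5. Record the change in SAP 10, which does not mention it now.

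The cost is SAP wording, the reconciliation with the protocol, and somewhat more table programming, including delayed entry for re-assigned participants. AEs are already collected from the first study-mandated procedure. The polyTreg safety display may look less favourable as a result.
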